Procedure or Assessment	Screening (Day -30 to Day -1)	W1D1	W2D1	W4D1	W4D2	Q3W (W7D1, W10D1, etc.)	End of Treatment (EOT) ^a	30-Day Safety Follow-up (30DFU) ^b	Posttreatment Follow-up (PTFU) ^c (Q3mo)	Long-Term Survival Follow-up (LTSFU) ^d (Q3mo)
Visit Windows	n/a	n/a	-2/+5d	+3d	n/a	± 3d	+7d	+7d	± 2 weeks	± 4 weeks
CMP-001 Injection (Dose Number) ^e		1 SC/IT	2	3		4+				
Pembrolizumab Dosing (Dose Number) ^f		1		2		3+				
Thyroid Function Tests ^l	X			X		X	X			
Autoimmune Laboratory Panel ^l	X						X			
Pregnancy Test and Follicle Stimulating Hormone ^l	X	X		X		X	X			
Exploratory Biomarker Sampling ^m		X		X	X	W7D1				
Exploratory Sampling for Pharmacokinetics ^m		X		X	X	W7D1				
Tumor Biopsy (known PD-L1 status) ⁿ	X					W7D1				
Blood Sampling for Cytokine and Complement ^o		X		X		W7D1				
Disease Assessment (Radiographic Imaging) ^p	X					W10D1 Q9W	X		X	
Disease Assessment (CNS Imaging) ^p	X					W10D1 Q9W	X		X	
Photographic Imaging ^q	X					W10D1 Q9W	X		X	
30-Day Follow-Up (Office or Phone Call)								X		
Long-Term Survival Follow-up Phone Call										X

Abbreviations: 30DFU = 30-day follow-up; CNS = central nervous system; CPS = combined positive score; D = day; ECG = electrocardiogram; ECOG = Eastern Cooperative Oncology Group; EOT = end of treatment; FSH = follicle stimulating hormone; HPV = human papillomavirus; iRECIST = immunotherapy Response Evaluation Criteria in Solid Tumors; LTSFU = long-term survival follow-up; MRI = magnetic resonance imaging; PTFU = posttreatment follow-up; RECIST = Response Evaluation Criteria in Solid Tumors; Q3W = every 3 weeks; W = week; WOCBP = women of child bearing potential.

a. EOT assessments to be performed within 7 days following subject discontinuation from study treatment. Removal of a subject from CMP-001 treatment is defined as the time in which the Investigator decides to discontinue study treatment. If a subject has CMP-001 dosing withheld for more than 3 consecutive doses for any reason during the Q3W dosing period, resumption of treatment must be discussed with the Medical

Amendment 2 (Version 3.0)

14 January 2022

13

Confidential

Monitor; otherwise, the subject will be discontinued from study treatment and will have all EOT assessments performed. End of Treatment occurs once the subject discontinues administration of CMP-001. Subjects can continue to receive pembrolizumab as standard of care but will no longer be considered in study treatment.

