Stop dates of AEs / Concomitant Medications will be imputed as follows:

- Completely missing stop date will not be imputed.
- Stop date missing both the month and day will be imputed as Dec 31st of the year of stop date.
- Stop date missing the day will be imputed as the last date of the month of the stop date.
- After imputation, the imputed date will be compared against the date of death, if available. If the planned imputed date is later than the date of death, the date of death will be used as the imputed date instead. If there is no date of death in the EDC for a subject and the planned imputed date is later than the End-of-Treatment (the last drug received) date + 30 days, then the End-of-Treatment (EOT of the last study drug received) date + 30 days will be used for the stop date.

Missing Dates in Prior Medications

Start or Stop dates of Prior Medications will be imputed as follows:

- Completely missing start or stop date will not be imputed.
- Start or stop date with missing both the month and day will be imputed as Dec 31st of the year of stop date.
- Start date missing the day will be imputed as the 1st of the month of the start date.
- Stop date missing the day will be imputed as the last date of the month of the stop date or the study first dose date, whichever comes earlier.

D. Multiple Study Centers

No adjustment for study center is planned.

E. Covariate Adjustment in Primary Analysis

No covariate adjustments are planned.

F. Sample Size Reassessment

Not applicable.

Regeneron Pharmaceuticals Inc. / Protocol: CMP-001-007
IQVIA Biotech (Confidential) Project # SZA56629

G. Ad-hoc Analyses

There will be an ad-hoc analysis planned with the trigger event being two disease assessments after the enrollment of the last subject. The ad-hoc analysis of the endpoints will follow the efficacy analysis methods described in Section **Error! Reference source not found.** below as well as the safety analysis methods detailed in Section **Error! Reference source not found.** below for the exploratory Phase 2 study.

The following unblinded subject information, efficacy-related and safety-related data displays will be produced for the purpose of the ad-hoc analysis. Unless stated otherwise, these displays are summary tables that summarize data for the corresponding analysis set:

- Subject information
 - Demographics
 - Baseline characteristics
 - Disposition
 - Medical history
 - Cancer history
 - ECOG
- Efficacy

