As of the data cutoff date, the number and percentage of subjects who screen fail and enroll in the study (receive at least one dose of study treatment), discontinue study treatment, and discontinue the study will be summarized for all screened subjects. The primary reason for treatment(s) and study discontinuation will also be summarized for Treated Analysis Set. Additionally, subgroup analysis of disposition by schedule will also be performed. Subject disposition will be presented in a by-subject data listing.

Study treatment (CMP-001 only or both CMP-001 and Pembrolizumab) may be discontinued for any of the following occurrences:

- Adverse Event
- PD per RECIST v1.1
- Subject Achieved and Maintained a Confirmed CR or iCR (and has been treated for at least 24 weeks, and has received at least 2 doses of both study treatments beyond the date of initial CR/iCR)
- Upon Request of the Sponsor or Regulatory Agency

Regeneron Pharmaceuticals Inc. / Protocol: CMP-001-007
IQVIA Biotech (Confidential) Project # SZA56629

- Clinical Disease Progression
- Medically Necessary in the Opinion of the Investigator
- Subject Withdrew Consent for Treatment
- Subject Became Pregnant or Began Breastfeeding
- Subject Lost to Follow-up
- Death
- Subject Completed 2 Years of Study Treatment
- End of Clinical Trial
- Other

Study Participation may be discontinued for any of the following occurrences:

- Completed
- Adverse Event
- Subject Withdrew Consent
- Lost to Follow-Up
- Death
- Study Terminated by Sponsor
- End of Clinical Trial
- Other

Percentages of subjects who withdrew for each of these reasons will be calculated using all members of the relevant analysis set for the denominator.

C. Protocol Deviations and Population Inclusions

All protocol deviations will be captured electronically outside of the Electronic Data Capture (EDC) system in the IQVIA Biotech IL-2 system and presented in a by-subject data listing. All deviations will be reviewed on an ongoing basis and classified as major or minor following study review process.

VIII. Efficacy Analyses

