All events of RECIST v1.1 disease progression or death will be counted regardless of whether the event occurred while the subject was on study drug or had previously discontinued treatment. Subjects who do not experience disease progression or death before the analysis cutoff date will be censored at the date of last adequate tumor assessment. Date of censoring for these subjects will be based on the last tumor assessment prior to missing the assessments. For subjects who started a subsequent anti-cancer therapy before having a documented PD, the overall response assessment evaluated after new anti-cancer treatment will not be considered for PFS calculation, and the last disease assessment prior to the start of the subsequent therapy will be used. Censoring rules are summarized in Table 1a. If a subject meets the criteria for more than one censoring rule, PFS will be censored at the earliest censoring date.

Overall Survival (OS). Overall survival will be calculated as the time from first dose of study treatment to the date of death due to any cause. Subjects who are alive at the time of analyses will be censored at the time of last known alive date, or at data cutoff date, whichever occurs first. Censoring rules are detailed in Table 1c. The last contact date will be derived as [Table 2](#).

Regeneron Pharmaceuticals Inc. / Protocol: CMP-001-007
IQVIA Biotech (Confidential) Project # SZA56629

OS will be calculated as follows:

$$\text{OS (months)} = (\text{Death or Censoring Date} - \text{First Dose Date} + 1) / 30.4375$$

Immune Objective Response Rate (iORR). iORR is defined as the proportion of subjects with a best overall immune response (iBOR) of confirmed immune complete response (iCR) or confirmed immune partial response (iPR) based on immunotherapy Response Evaluation Criteria in Solid Tumors (iRECIST) by Investigator assessment.

Subjects who continue study treatment beyond PD per RECIST v1.1 will be assessed by the Investigator according to iRECIST. Subjects with an iCR or iPR per iRECIST must have a confirmatory assessment performed at least 4 weeks after the initial assessment where response was declared by the Investigator and all scans should be performed at least 2 weeks after the previous CMP-001 IT injection to prevent injection-related pseudo-progression.

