iUPD per iRECIST, continued study treatment with subsequent disease assessments but no confirmed PD (i.e., iCPD not assigned) or Death as of data cutoff date and subject not received new anticancer therapy or received it after the data cutoff date	Censored	Date of the last tumor assessment as of data cutoff date	Alive without Documented iCPD
iUPD per iRECIST, continued study treatment, but started a new anti-cancer therapy before data cutoff date without evidence of iCPD or Death	Censored	Date of the last tumor assessment prior to new anti-cancer therapy	Subsequent Anti-cancer Therapy without Documented iCPD
iCPD per iRECIST or Death after new anticancer therapy and the new anticancer started before data cutoff date	Censored	Date of last disease assessment prior to new anticancer therapy	iCPD or Death after Subsequent Anti-cancer Therapy
iCPD per iRECIST or Death after new anticancer therapy and the new anticancer started after data cutoff date	Censored	Date of last disease assessment on/before data cutoff date	iCPD or Death after Subsequent Anti-cancer Therapy
iUPD per iRECIST, continued study treatment, iCPD or Death immediately following two or more consecutive disease assessments since the last adequate disease assessment	Censored	Date of last adequate tumor assessment prior to the first missed assessment	iCPD or Death after Missing ≥ 2 Consecutive Disease Assessments
Withdraw consent or lost to follow-up before iCPD per iRECIST or death	Censored	Date of last adequate disease assessment	Discontinued from Study without Documented iCPD or Death

Table 1c: Censoring Rules for the OS

Situation	Outcome	Date	Event Description/ Censoring Reason
Death on/before data cutoff date	Event	Date of death	Death
Alive with study completed before data cutoff date	Censored	Study completion date	Alive on or before study completion date
Alive or death after data cutoff date with study continuing on/till after data cutoff date	Censored	Data cutoff date	Alive on or before data cutoff date

Regeneron Pharmaceuticals Inc. / Protocol: CMP-001-007
 IQVIA Biotech (Confidential) Project # SZA56629

Lost to follow-up prior to data cutoff date	Censored	Last known alive date	Discontinued from study
Discontinued study without death and not lost to follow-up on/prior to data cutoff date	Censored	Date of study discontinuation	Discontinued from study

Table 2: Last Contact Date for the Overall Survival

Source Data	Conditions

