Last date patient known to be alive from Long-Term Follow-Up eCRF	Use if patient status is reported to be alive. Do not use if patient status is not reported unknown
Post-treatment follow-up eCRF questions	Use if record selected
End of study	Not lost to follow up
Start/end dates from drug administration record	Nonmissing dose. Doses of 0 are allowed
Dosing prophylaxis eCRF	Prophylaxis given marked as yes
End of treatment date from the End of Treatment eCRFs	No condition
Tumor assessment (RECIST v1.1 or iRECIST) date	Evaluation is marked as done
Laboratory/PK collection dates	Sample collection marked as done
Vital signs date	At least 1 nonmissing parameter value
Physical examination	Evaluation performed marked as yes
12-Lead ECG	Evaluation performed marked as yes
ECOG performance status date	Nonmissing ECOG performance status
Start/end dates of adverse events	Nonmissing verbatim term
Start/end dates of concomitant medications and procedures	Nonmissing verbatim term

B. Primary Efficacy Analysis

The primary efficacy endpoint of ORR: The two-sided 95% CIs for the point estimates will be provided using Clopper-Pearson method.

A table summarizing the number and percentage of subjects with a Best Overall Response (BOR) of CR, PR, SD, PD, or Not Evaluable will be presented. This table will also include the ORR and DCR, with their two-sided 95% CI calculated using the Clopper-Pearson method.

Regeneron Pharmaceuticals Inc. / Protocol: CMP-001-007
IQVIA Biotech (Confidential) Project # SZA56629

C. Secondary Efficacy Analyses

The secondary efficacy endpoints include PFS, DOR, iORR, iPFS, iDOR and OS.

iORR. The two-sided 95% CIs for the point estimates will be provided using Clopper-Pearson method.

PFS, DOR, iPFS, iDOR, and OS. Estimates of median with 95% CIs will be computed using the Kaplan-Meier method. Kaplan-Meier curves will be plotted. Median Time-to-Event will be estimated at the 50th percentile of the corresponding Kaplan-Meier estimates. The event-free rate with the two-sided 95% CIs using Greenwood's formula will be calculated for 3-month interval timepoints (e.g., 6, 9, 12 and 18 months). The reasons for censoring will be summarized categorically with the number and percentage of subjects tabulated.

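### SAP Table 2 sets no loss-to-follow-up condition on the End of Treatment date, so OS may be censored slightly late for subjects lost during treatment

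*SAP*

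**What the plan says.** SAP section VIII.A (Overall Survival) states: "Subjects who are alive at the time of analyses will be censored at the time of last known alive date", or at data cutoff if that comes sooner. The same paragraph refers to Table 2 with the words "The last contact date will be derived as". Table 1c uses the last known alive date in one row only, "Lost to follow-up prior to data cutoff date". Its other rows censor living subjects at study completion, data cutoff or study discontinuation.

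Table 2 lists source dates, each with a condition. For the End of study date the condition is "Not lost to follow up". For "End of treatment date from the End of Treatment eCRFs" the condition cell says that there is none. SAP section VII.B lists "Subject Lost to Follow-up" among the reasons why treatment may end, and Protocol section 4.5 does the same.

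The documents describe the end of treatment in more than one way. Protocol Table 1, note a, says: "Removal of a subject from CMP-001 treatment is defined as the time in which the Investigator decides to discontinue study treatment". SAP section VI.C, in its rule for AE and medication stop dates, instead explains End of Treatment by reference to the last drug received.

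**The concern.** For a subject who stops attending, the study-end date is probably the day the site records the loss, not a day on which the subject was known to be alive. The SAP does not give its reason for restricting the End of study row, but this is the natural one. The EOT date is open to the same objection when treatment ends through loss to follow-up, and there the restriction is absent.

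If the EOT date falls after the last real contact, the subject stays in the OS risk set, counted as event-free, during time when nobody knew the vital status. The gap in the rule falls on the one group that Table 1c sends to this derivation. The SAP plans an OS median, landmark rates and an analysis by dosing schedule, and all of these use the same censoring dates.

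**Working it through.** **1. Who is affected.** Lost subjects are the only Table 1c group censored at the last known alive date. A death on or before cutoff is an event at its own date. The EOT row therefore matters only for a subject lost during treatment whose EOT date is later than every other qualifying Table 2 date. That the last known alive date is the Table 2 last contact date is implied, not stated; SAP section VI.C uses both terms in its rules for partial death dates.

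**2. What the EOT date is.**
- Protocol Table 1, note a, ties removal from CMP-001 to the Investigator's decision. It also says that End of Treatment occurs when CMP-001 administration is discontinued.
- SAP section VI.C refers to the last drug received. This could mean the last dose date, or the EOT date of whichever drug ended last.
- SAP section IX.A.1 computes duration from the earlier of last dose + 21 days and the discontinuation or completion date, so it treats discontinuation and last dose as different dates.

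The documents leave the definition open.

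**3. What the row adds.** If the EOT date is the last dose, the drug administration row already supplies it. If it is an attended EOT visit, the vital signs, examination, ECG, ECOG and laboratory rows would normally supply it, since Protocol Table 1 schedules all of these at EOT. The row therefore usually moves a censoring date only when no dose or assessment is recorded that day.

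**4. Direction.** At each death the Kaplan-Meier estimate is multiplied by 1 − 1/n, with n the number at risk. Keeping a lost subject in the risk set increases n. If one of 24 subjects is lost and the first death falls in the gap, the factor is 1 − 1/24 = 0.9583 instead of 1 − 1/23 = 0.9565. No event can be observed for the lost subject in the gap, so the curve stays equal or rises.

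**5. Size.** Neither document gives a planning figure for OS or a number lost, so there is no stated figure to reproduce.

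From the documents:
- 24 treated subjects (39 screened − 15 screen failures, SAP section II.C).
- Median OS of 10.7 or 14.9 months, the two values in Protocol section 1.1 for the comparator and for pembrolizumab monotherapy in the cited phase 3 trial.

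Assumed:
- 1, 2 or 4 subjects lost on treatment, with last contact uniform over months 1 to 11.
- A gap of 3, 9 or 12 weeks, that is 1, 3 or 4 missed three-weekly visits. In months this is weeks × 7 / 30.4375 = 0.69, 2.07 or 2.76.
- Exponential survival, with the other subjects administratively censored uniformly over months 12 to 30.

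Each of 3,000 simulated trials per scenario was analysed twice, with lost subjects censored at last contact and at last contact plus the gap. The median shift uses runs in which both medians were reached. Mean shifts for gaps of 3 / 9 / 12 weeks:

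| Median OS | Lost | 12-month OS (points) | Median OS (months) |
|---|---|---|---|
| 10.7 | 1 | 0.14 / 0.40 / 0.52 | 0.00 / 0.00 / 0.00 |
| 10.7 | 2 | 0.26 / 0.80 / 1.06 | 0.01 / 0.03 / 0.05 |
| 10.7 | 4 | 0.53 / 1.63 / 2.10 | 0.17 / 0.46 / 0.58 |
| 14.9 | 1 | 0.10 / 0.32 / 0.40 | 0.01 / 0.03 / 0.03 |
| 14.9 | 2 | 0.21 / 0.63 / 0.82 | 0.03 / 0.11 / 0.14 |
| 14.9 | 4 | 0.42 / 1.25 / 1.62 | 0.12 / 0.39 / 0.58 |

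No run gave a negative shift. The largest single-run shift in 12-month OS was 7.4 points (4 lost, 12 weeks). For scale, the binomial standard error of a 50% rate with 24 subjects is √(0.5 × 0.5 / 24) = 0.102, about 10 points.

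**The case against.** The strongest reply is that SAP section VI.C explains End of Treatment by the last drug received, and the SAP states that it governs where it differs from the protocol. If that means the last dose date, it is a contact with a living subject and the bias disappears. This stands as a possible reading. It is not the only one, and on that reading the EOT row adds nothing, so restricting it costs nothing.

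It is also fair to say that no document shows an affected subject, that the shift is small against a standard error near 10 points, and that SAP section II.C makes all analyses descriptive and exploratory. All of this stands and limits the weight of the point.

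A reader might infer more than the documents support:
- *That every gap would be 12 weeks or longer.* The rule on more than 3 consecutive withheld doses (Protocol section 5.1.2.4) concerns resuming treatment and does not define loss to follow-up. Adding the 30-day allowance of SAP section VI.C to a 12-week gap is not justified either, because that same rule describes EOT by the last drug received.
- *That zero-dose records create false contacts.* Table 2 accepts them, but nothing shows that an unattended visit produces a dated zero-dose record. Protocol section 5.4 handles fully missed visits through source documents and protocol deviations.
- *That imputed stop dates certainly enter Table 2 and distort partial death dates.* SAP section VI.C does say "Stop date missing the day will be imputed as the last date of the month of the stop date", and Table 2 does not exclude imputed AE or medication dates. But it does not call for them, the SAP default is no imputation unless stated, and imputed stop dates later than an available death date are replaced by it. How that works with a partial death date is unclear, so an error is possible but not demonstrated.

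**Conclusion.** The inconsistency between the two Table 2 rows is real, and its possible effect runs in one direction: OS may be slightly too high. The documents do not support saying that OS is biased upward as a fact. That would require a subject lost during treatment, an EOT date that is a decision date and not a dose or visit, and no later qualifying contact.

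Under the stated assumptions the mean shift in 12-month OS is 0.1 to 0.5 points with 1 of 24 lost, 0.2 to 1.1 with 2 and 0.4 to 2.1 with 4. The mean shift in the median is at most 0.03, 0.14 and 0.58 months respectively. Schedule subgroups are smaller, so one such subject would weigh more there; the documents do not give the split, so this is not quantified. If nobody is lost on treatment, or if EOT is the last dose date, the row has no effect. This is a minor point, worth correcting because the correction is simple.

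**What to change.** 1. In Table 2, accept the EOT date only if the reason for ending treatment is not loss to follow-up, matching the End of study row. The row refers to more than one form, so apply the condition to each.
2. State whether the EOT date is the last dose, the EOT visit or the discontinuation decision.
3. State that the last known alive date in Table 1c is the latest qualifying Table 2 date.
4. As a secondary safeguard, use only reported, non-imputed AE, medication and procedure dates in Table 2, and derive last contact before any imputation.

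The cost is a few lines of text and minor programming; SAP section VII.B already summarises the reason for ending treatment. A few OS censoring times become slightly shorter. A genuine contact would be lost only if it took place on the EOT date and left no other qualifying record.
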